9.5. Interim Analysis

No formal interim analysis will be conducted for this study. However, as this is an open-label study, the sponsor may conduct unblinded reviews of the data during the course of the study for the purpose of safety assessment, facilitating dose-escalation decisions, facilitating PK/PD modeling, and/or supporting clinical development.

9.6. Data Monitoring Committee

This study will not use a data monitoring committee (DMC).

10. QUALITY CONTROL AND QUALITY ASSURANCE

Pfizer or its agent will conduct periodic monitoring visits during study conduct for studies conducted at non-Pfizer investigator sites, to ensure that the protocol and Good Clinical Practices (GCPs) are being followed. The monitors may review source documents to confirm that the data recorded on CRFs are accurate. The investigator and institution will allow Pfizer monitors/auditors or its agents and appropriate regulatory authorities direct access to source documents to perform this verification. This verification may also occur after study completion.

During study conduct and/or after study completion, the investigator site may be subject to review by the IRB/EC, and/or to quality assurance audits performed by Pfizer, or companies working with or on behalf of Pfizer, and/or to inspection by appropriate regulatory authorities.

The investigator(s) will notify Pfizer or its agents immediately of any regulatory inspection notification in relation to the study. Furthermore, the investigator will cooperate with Pfizer or its agents to prepare the investigator site for the inspection and will allow Pfizer or its agent, whenever feasible, to be present during the inspection. The investigator site and investigator will promptly resolve any discrepancies that are identified between the study data and the subject's medical records. The investigator will promptly provide copies of the inspection findings to Pfizer or its agent. Before response submission to the regulatory authorities, the investigator will provide Pfizer or its agents with an opportunity to review and comment on responses to any such findings.

For studies conducted at non-Pfizer investigator sites, it is important that the investigator(s) and their relevant personnel are available during the monitoring visits and possible audits or inspections and that sufficient time is devoted to the process.

11. DATA HANDLING AND RECORD KEEPING

11.1. Case Report Forms/Data Collection Tools/Electronic Data Record

As used in this protocol, the term CRF should be understood to refer to either a paper form or an electronic data record or both, depending on the data collection method used in this study.

A CRF is required and should be completed for each included subject. The completed original CRFs are the sole property of Pfizer and should not be made available in any form to third parties, except for authorized representatives of Pfizer or appropriate regulatory authorities, without written permission from Pfizer.

The investigator has ultimate responsibility for the collection and reporting of all clinical, safety, and laboratory data entered on the CRFs and any other data collection forms (source documents) and ensuring that they are accurate, authentic/original, attributable, complete, consistent, legible, timely (contemporaneous), enduring, and available when required. The CRFs must be signed by the investigator or by an authorized staff member to attest that the data contained on the CRFs are true. Any corrections to entries made in the CRFs or source documents must be dated, initialed, and explained (if necessary) and should not obscure the original entry.

In most cases the source documents are the hospital or the physician's chart. In these cases, data collected on the CRFs must match those charts.

In some cases, the CRF may also serve as the source document. In these cases, a document should be available at the investigator site and at Pfizer that clearly identifies those data that will be recorded on the CRF, and for which the CRF will stand as the source document.

11.2. Record Retention

To enable evaluations and/or inspections/audits from regulatory authorities or Pfizer, the investigator agrees to keep records, including the identity of all participating subjects (sufficient information to link records, eg, CRFs and hospital records), all original signed informed consent documents, copies of all CRFs, safety reporting forms, source documents, detailed records of treatment disposition, and adequate documentation of relevant correspondence (eg, letters, meeting minutes, and telephone call reports). The records should be retained by the investigator according to the ICH guidelines, according to local regulations, or as specified in the clinical study agreement (CSA), whichever is longer.

If the investigator becomes unable for any reason to continue to retain study records for the required period (eg, retirement, relocation), Pfizer should be prospectively notified. The study records must be transferred to a designee acceptable to Pfizer, such as another investigator, another institution, or to an independent third party arranged by Pfizer.

Investigator records must be kept for a minimum of 15 years after completion or discontinuation of the study or for longer if required by applicable local regulations.

The investigator must obtain Pfizer's written permission before disposing of any records, even if retention requirements have been met.

12. ETHICS

12.1. Institutional Review Board/Ethics Committee

It is the responsibility of the investigator to have prospective approval of the study protocol, protocol amendments, informed consent documents, and other relevant documents, eg, recruitment advertisements, if applicable, from the IRB/EC. All correspondence with the IRB/EC should be retained in the investigator file. Copies of IRB/EC approvals should be forwarded to Pfizer.

The only circumstance in which an amendment may be initiated prior to IRB/EC approval is where the change is necessary to eliminate apparent immediate hazards to the subjects. In that event, the investigator must notify the IRB/EC and Pfizer in writing immediately after the implementation.

12.2. Ethical Conduct of the Study

The study will be conducted in accordance with the protocol, legal and regulatory requirements, and the general principles set forth in the International Ethical Guidelines for Biomedical Research Involving Human Subjects (Council for International Organizations of Medical Sciences 2002), ICH Guideline for Good Clinical Practice, and the Declaration of Helsinki.

12.3. Subject Information and Consent

All parties will ensure protection of subject personal data and will not include subject names or other identifiable data in any reports, publications, or other disclosures, except where required by laws.

When study data are compiled for transfer to Pfizer and other authorized parties, subject names, addresses, and other identifiable data will be replaced by numerical codes based on a numbering system provided by Pfizer in order to de-identify study subjects. The investigator site will maintain a confidential list of subjects who participated in the study, linking each subject's numerical code to his or her actual identity. In case of data transfer, Pfizer will maintain high standards of confidentiality and protection of subjects' personal data consistent with applicable privacy laws.

The informed consent documents and any subject recruitment materials must be in compliance with ICH GCP, local regulatory requirements, and legal requirements, including applicable privacy laws.

The informed consent documents used during the informed consent process and any subject recruitment materials must be reviewed and approved by Pfizer, approved by the IRB/EC before use, and available for inspection.

The investigator must ensure that each study subject, is fully informed about the nature and objectives of the study and possible risks associated with participation.

The investigator, or a person designated by the investigator, will obtain written informed consent from each subject before any study-specific activity is performed. The investigator will retain the original of each subject's signed consent document.

12.4. Reporting of Safety Issues and Serious Breaches of the Protocol or ICH GCP

In the event of any prohibition or restriction imposed (ie, clinical hold) by an applicable regulatory authority in any area of the world, or if the investigator is aware of any new information that might influence the evaluation of the benefits and risks of the investigational product, Pfizer should be informed immediately.

In addition, the investigator will inform Pfizer immediately of any urgent safety measures taken by the investigator to protect the study subjects against any immediate hazard, and of any serious breaches of this protocol or of ICH GCP that the investigator becomes aware of.

13. DEFINITION OF END OF TRIAL

13.1. End of Trial in the United States

Last subject last visit (LSLV) is defined as the date the investigator reviews the last subject's final safety data and determines that no further evaluation is required for the subject to complete the trial.

14. SPONSOR DISCONTINUATION CRITERIA

Premature termination of this study may occur because of a regulatory authority decision, change in opinion of the IRB/EC, or investigational product safety problems, or at the discretion of Pfizer. In addition, Pfizer retains the right to discontinue development of lorlatinib at any time.

If a study is prematurely terminated, Pfizer will promptly notify the investigator. After notification, the investigator must contact all participating subjects and the hospital pharmacy (if applicable) within 7 days. As directed by Pfizer, all study materials must be collected and all CRFs completed to the greatest extent possible.

15. PUBLICATION OF STUDY RESULTS

15.1. Communication of Results by Pfizer

Pfizer fulfills its commitment to publicly disclose clinical study results through posting the results of studies on www.clinicaltrials.gov (ClinicalTrials.gov), the European Clinical Trials Database (EudraCT), and/or www.pfizer.com, and other public registries in accordance with applicable local laws/regulations.

In all cases, study results are reported by Pfizer in an objective, accurate, balanced, and complete manner and are reported regardless of the outcome of the study or the country in which the study was conducted.

www.clinicaltrials.gov

Pfizer posts clinical trial US Basic Results on www.clinicaltrials.gov for Pfizer-sponsored interventional studies (conducted in patients) that evaluate the safety and/or efficacy of a Pfizer product, regardless of the geographical location in which the study is conducted. US Basic Results are submitted for posting within 1 year of the primary completion date (PCD) for studies in adult populations or within 6 months of the PCD for studies in pediatric populations.

PCD is defined as the date that the final subject was examined or received an intervention for the purposes of final collection of data for the primary outcome, whether the clinical study concluded according to the prespecified protocol or was terminated.

EudraCT

Pfizer posts European Union (EU) Basic Results on EudraCT for all Pfizer-sponsored interventional studies that are in scope of EU requirements. EU Basic Results are submitted for posting within 1 year of the PCD for studies in adult populations or within 6 months of the PCD for studies in pediatric populations.

www.pfizer.com

Pfizer posts public disclosure synopses (CSR synopses in which any data that could be used to identify individual patients have been removed) on www.pfizer.com for Pfizer-sponsored interventional studies at the same time the US Basic Results document is posted to www.clinicaltrials.gov.

15.2. Publications by Investigators

Pfizer supports the exercise of academic freedom and has no objection to publication by the principal investigator (PI) of the results of the study based on information collected or generated by the PI, whether or not the results are favorable to the Pfizer product. However, to ensure against inadvertent disclosure of confidential information or unprotected inventions, the investigator will provide Pfizer an opportunity to review any proposed publication or other type of disclosure of the results of the study (collectively, "publication") before it is submitted or otherwise disclosed.

The investigator will provide any publication to Pfizer at least 30 days before it is submitted for publication or otherwise disclosed. If any patent action is required to protect intellectual property rights, the investigator agrees to delay the disclosure for a period not to exceed an additional 60 days.

The investigator will, on request, remove any previously undisclosed confidential information before disclosure, except for any study- or Pfizer product-related information necessary to the appropriate scientific presentation or understanding of the study results.

If the study is part of a multicenter study, the investigator agrees that the first publication is to be a joint publication covering all investigator sites, and that any subsequent publications by the PI will reference that primary publication. However, if a joint manuscript has not been submitted for publication within 12 months of completion or termination of the study at all participating sites, the investigator is free to publish separately, subject to the other requirements of this section.

For all publications relating to the study, the institution will comply with recognized ethical standards concerning publications and authorship, including Section II - "Ethical Considerations in the Conduct and Reporting of Research" of the Uniform Requirements for Manuscripts Submitted to Biomedical Journals, <http://www.icmje.org/index.html#authorship>, established by the International Committee of Medical Journal Editors.

Publication of study results is also provided for in the CSA between Pfizer and the institution. In this section entitled **Publications by Investigators**, the defined terms shall have the meanings given to them in the CSA.

If there is any conflict between the CSA and any attachments to it, the terms of the CSA control. If there is any conflict between this protocol and the CSA, this protocol will control as to any issue regarding treatment of study subjects, and the CSA will control as to all other issues.

Appendix 1. Abbreviations

The following is a list of abbreviations that may be used in the protocol.

| Abbreviation | Term |
|--------------------------------|---|
| Abs | Absolute |
| ADME | absorption, distribution, metabolism, excretion |
| Ae | cumulative amount of drug recovered unchanged in the urine, from zero to time 120 hours post-dose |
| Ae% | cumulative amount of drug recovered unchanged in the urine, from zero to time 120 hours post-dose, expressed as fraction of administered dose |
| AE | adverse event |
| ALK | Anaplastic Lymphoma Kinase |
| ALT | alanine aminotransferase |
| ANOVA | analysis of variance |
| AST | aspartate aminotransferase |
| ATP | adenosine triphosphate |
| AUC | area under the curve |
| AUC ₂₄ | area under the concentration-time curve from time 0 to 24 hours |
| AUC _{inf} | area under the plasma concentration-time curve from time 0 extrapolated to time infinity |
| AUC _{last} | area under the concentration-time curve from time 0 to the time of the last quantifiable concentration |
| AV | Atrioventricular |
| AVB | atrioventricular block |
| BA | Bioavailability |
| CCI | |
| BID | twice a day |
| BMI | body mass index |
| BP | blood pressure |
| bpm | beats per minute |
| BSA | body surface area |
| BUN | blood urea nitrogen |
| C _b /C _p | blood to plasma concentration ratios |
| C _{eff} | efficacious concentration |
| CHO | Chinese Hamster Ovary |
| CI | confidence interval |
| CK | creatine kinase |
| CL | Clearance |
| CL _{cr} | creatinine clearance |
| CL/F | apparent clearance after oral dose |
| CL _r | renal clearance |
| C _{max} | peak or maximum observed concentration |

| Abbreviation | Term |
|------------------|--|
| CNS | central nervous system |
| CO ₂ | carbon dioxide (bicarbonate) |
| CRF | case report form |
| CRM | continual reassessment method |
| CRU | clinical research unit |
| CSA | clinical study agreement |
| CSF | cerebrospinal fluid |
| CSR | clinical study report |
| CT | clinical trial |
| CTC | Common Terminology Criteria |
| %CV | coefficient of variation |
| CYP | cytochrome P450 |
| DCT | data collection tool |
| DDI | drug-drug-interaction |
| DILI | drug-induced liver injury |
| DLT | dose limiting toxicities |
| DMC | data monitoring committee |
| DNA | deoxyribonucleic acid |
| EC | ethics committee |
| ECG | Electrocardiogram |
| EDP | exposure during pregnancy |
| eGFR | estimated glomerular filtration rate |
| EML4 | echinoderm microtubule-associated protein-like 4 |
| EU | European Union |
| EudraCT | European Clinical Trials Database |
| FDA | Food and Drug Administration |
| FISH | fluorescent in situ hybridization |
| FOB | functional observation battery |
| FSH | follicle-stimulating hormone |
| f _u | fraction unbound |
| GCP | Good Clinical Practice |
| GFR | glomerular filtration rate |
| GGT | gamma-glutamyl transferase |
| HCVAb | hepatitis C antibody |
| HepBcAb | hepatitis B core antibody |
| HepBsAg | hepatitis B surface antigen |
| hERG | human ether-a-go-go related gene |
| HIV | human immunodeficiency virus |
| HLM | human liver microsomes |
| IB | Investigator's Brochure |
| IC ₅₀ | 50% inhibitory concentration |
| ICH | International Council on Harmonisation |

| Abbreviation | Term |
|-----------------------|---|
| ID | Identification |
| IND | investigational new drug application |
| INR | international normalized ratio |
| IRB | institutional review board |
| IUD | intrauterine device |
| IV | Intravenous |
| K ₂ EDTA | dipotassium ethylenediaminetetraacetic acid |
| LOAEL | lowest observed adverse effect level |
| LFT | liver function test |
| LSLV | last subject last visit |
| MCH | mean corpuscular hemoglobin |
| MCHC | mean corpuscular hemoglobin concentration |
| MCV | mean corpuscular volume |
| MDCK-MDR1 | Madin Darby canine kidney with multidrug resistance protein 1 |
| MDRD | Modification of Diet in Renal Disease |
| MRAUC _{inf} | metabolite(s) to parent ratio for AUC _{inf} |
| MRAUC _{last} | metabolite(s) to parent ratio for AUC _{last} |
| MRC _{max} | metabolite(s) to parent ratio for C _{max} |
| mRNA | messenger ribonucleic acid |
| MTD | maximum tolerated dose |
| MW | molecular weight |
| N/A | not applicable |
| NADPH | nicotinamide adenine dinucleotide phosphate |
| NOEL | no observed effect level |
| NSCLC | non-small-cell lung carcinoma |
| PCD | primary completion date |
| PD | pharmacodynamic(s) |
| PE | physical examination |
| P-gp | P-glycoprotein |
| PGx | pharmacogenomic(s) |
| pH | potential of hydrogen |
| PI | principal investigator |
| PK | pharmacokinetic(s) |
| PPI | proton pump inhibitor |
| PT | prothrombin time |
| QD | once daily |
| QTc | corrected QT |
| qual | Qualitative |
| R _{ac} | observed accumulation ratio |
| RBC | red blood cell |
| ROS1 | c-ros oncogene 1 |
| RP2D | recommended Phase 2 dose |

| Abbreviation | Term |
|----------------------|--|
| RNA | ribonucleic acid |
| R _{ss} | steady state accumulation ratios |
| RTK | receptor tyrosine kinases |
| SAE | serious adverse event |
| SAP | statistical analysis plan |
| S _{Cr} | serum creatinine |
| S _{cr, std} | serum creatinine measured with a standardized assay for serum creatinine |
| SOP | standard operating procedure |
| SRSD | single reference safety document |
| t _½ | terminal plasma elimination half-life |
| TBili | total bilirubin |
| THC | Tetrahydrocannabinol |
| TKI | tyrosine kinase inhibitor |
| T _{max} | time for C _{max} |
| ULN | upper limit of normal |
| US | United States |
| V _{z/F} | volume of distribution |
| WBC | white blood cell |

1. AMENDMENTS FROM PREVIOUS VERSION(S)

None.

2. INTRODUCTION

In this study, the PK of lorlatinib after a single oral dose of lorlatinib will be evaluated in non-cancer subjects with normal renal function, mild renal impairment (defined as $CL_{cr} \geq 60$ mL/min and $CL_{cr} < 90$ mL/min), moderate renal impairment (defined as $CL_{cr} \geq 30$ mL/min and $CL_{cr} < 60$ mL/min), and severe renal impairment (defined as $CL_{cr} < 30$ mL/min not requiring dialysis) who are otherwise healthy. Data from this study would allow for the estimation of any changes in lorlatinib plasma exposure with varying extent of renal impairment.

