In this study, the PK of lorlatinib after a single oral dose of lorlatinib will be evaluated in non-cancer subjects with normal renal function, mild renal impairment, moderate renal impairment (defined as estimated glomerular filtration rate [eGFR] \geq 30 mL/min and eGFR $<$ 60 mL/min), and severe renal impairment (defined as eGFR $<$ 30 mL/min not requiring dialysis) who are otherwise healthy. Data from this study would allow for the estimation of any changes in lorlatinib plasma exposure with varying extent of renal impairment.

CCI

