2.1. Study Design

This will be a Phase 1, open-label, multi-center, single treatment study in subjects with normal renal function and varying degrees of renal impairment. Each subject will receive a single oral dose of lorlatinib administered in the fasted state.

This study is aimed toward enrolling approximately 32 evaluable subjects who complete the PK assessments. Subjects with the following renal function will be enrolled (Table 1).

Table 1. Group Assignment Based on Creatinine Clearance Estimates

Group	Description	Estimated eGFR
A (n=8)	Normal	≥ 90 mL/min
B (n=8)	Mild Renal Impairment	≥ 60- < 90 mL/min
C (n=8)	Moderate Renal Impairment	≥ 30- < 60 mL/min
D (n=8)	Severe Renal Impairment	< 30 mL/min and not requiring dialysis

Subjects who do not complete all PK collections may be replaced to ensure 8 evaluable subjects in Groups A, B, and C and at least 4 evaluable subjects in Group D.

Estimated glomerular filtration rate (eGFR) will be calculated using the MDRD equation as follows:

$$eGFR \text{ (mL/min/1.73m}^2\text{)} = 175 \times (S_{cr, \text{std}})^{-1.154} \times (\text{Age})^{-0.203} \times (0.742 \text{ if female}) \times (1.212 \text{ if African American})$$

where $S_{cr, std}$ denotes serum creatinine measured with a standardized assay for serum creatinine. Note that the value of eGFR, which is directly obtained from the lab or calculated using the equation above, is generally normalized to an average body size of 1.73 m^2 for diagnosis, prognosis and treatment of renal disease. In terms of clearance of renally filtrated drugs (including secreted drugs), renal elimination capacity is related to absolute glomerular filtration rate (GFR) in mL/min. The MDRD-derived, body surface area (BSA)-adjusted value of eGFR used to obtain absolute GFR (mL/min) for renal disease classification or subject assignment into different renal disease groups should be multiplied by the individual subject's normalized body surface area (ie, measured $BSA/1.73 \text{ m}^2$). The BSA of an individual will be calculated by the following formula as described below:

$$BSA = (\text{Weight}^{0.425} \times \text{Height}^{0.725}) \times 0.007184$$

In addition CL_{cr} will be calculated using the Cockcroft-Gault equation as follows:

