$$CL_{cr} \text{ (mL/min)} = \frac{[140 - \text{age (years)}] \times \text{total body weight (kg)} \times (0.85 \text{ for females})}{72 \times \text{serum creatinine (mg/dL)}}$$

Subjects will need to demonstrate stable renal function during the screening period within approximately a 2-week timeframe prior to dosing. Stable renal function is defined as 2 eGFR values obtained at least 3 days but not more than 14 days apart being within 25% of each other. The average value of the 2 eGFR values will be used for study enrollment and initial renal function stratification. The eGFR value within 24 hours prior to lorlatinib dosing will be the value used for final subject stratification, group assignment, and PK analysis. The CL_{cr} value will be recorded at the same time eGFR is determined. The CL_{cr} value on Day -1 (calculated by Cockcroft-Gault equation) will be calculated and recorded.

In order to safeguard subject safety, this study will enroll subjects with renal impairment in a staggered fashion. A single oral dose of 100 mg lorlatinib will be administered first to subjects with mild renal impairment (Group B). After single 100 mg oral dose of lorlatinib is tolerated in at least 3 subjects with mild renal impairment, subjects with moderate renal impairment (Group C) will be enrolled one at a time and administered a single oral dose of lorlatinib. There will be an observation period of at least 1 week after dosing of the first 3 subjects to evaluate safety and tolerability. Based on the safety and tolerability of the first 3 subjects in Group B, a dose lower than 100 mg of lorlatinib may be considered for Group C, as determined by the Sponsor. After dosing of 3 moderate renal impairment subjects, the PK, safety, and tolerability will be evaluated during an observation period of at least 1 week to confirm whether the selected dose is appropriate. If yes, the remaining subjects in Group C and the subjects in severe group (Group D) will be enrolled and dosed at the same dose. If not, a new, lower dose will be proposed for the remaining subjects in Group C and all subjects in Group D based on available information.

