8. STATISTICAL METHODOLOGY AND STATISTICAL ANALYSES

8.1. Statistical Methods

The relationship between PK parameters and renal function (eGFR) will be determined by a linear regression model.

The effect of the renal impairment on PK parameters will be assessed by constructing 90% confidence intervals around the estimated difference between each of the Test (renally impaired groups) and the Reference (normal renal function group) using a one-way ANOVA model based on natural log transformed data.

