8.2. Statistical Analyses

Analysis of variance (ANOVA) will be used to compare the natural log transformed AUC_{inf} (if data permit), AUC_{last} and C_{max} between the normal renal function group and each of the renal impairment groups. If a mixture of doses are used within the study, then the previous analysis will utilize dose normalized PK parameters instead. Point estimates and associated 90% confidence intervals (CIs) for the difference of each comparison will be estimated and exponentiated to provide geometric mean ratios and associated 90% CIs.

Regression analysis will be conducted to characterize the relationship between renal function and PK parameters CL/F and CL_R . Both eGFR obtained from the MDRD equation and CL_{Cr} calculated from the C-G formula on Day -1 will be used in regression analysis. Analysis results will include estimates of parameters for the chosen model as well as measures of precision such as CI or standard errors. PK parameters AUC_{inf} , C_{max} , AUC_{last} , time for C_{max} (T_{max}), terminal plasma elimination half-life ($t_{1/2}$), CL/F , CL_R , V_z/F , cumulative amount of drug recovered unchanged in the urine, from zero to time 120 hours post-dose (Ae), cumulative amount of drug recovered unchanged in the urine, from zero to time 120 hours post-dose, expressed as fraction of administered dose ($Ae\%$), will be summarized descriptively by analyte (eg, lorlatinib and its metabolite(s)) and renal function group.

Metabolite(s) to parent ratio for C_{max} (MRC_{max}), metabolite(s) to parent ratio for AUC_{last} ($MRAUC_{last}$), and metabolite(s) to parent ratio for AUC_{inf} ($MRAUC_{inf}$) will also be summarized descriptively by renal function group.

For AUC_{inf} , AUC_{last} and C_{max} , box-whisker plots of the parameters will be plotted by analyte and renal function group and overlaid with geometric means. Individual concentrations will be listed and summarized descriptively by group and PK sampling time. Individual subject and summary profiles (means and medians) of the concentration-time data will be plotted across different groups.

For summary statistics and summary plots by renal function group and sampling time, the nominal PK sampling time will be used; for individual subject plots by time, the actual PK sampling time will be used.

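### Does the SAP define the renal groups by creatinine clearance instead of MDRD eGFR, and does it leave the scale of the eGFR regressor open?

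*SAP*

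**What the plan says.** **Where creatinine clearance is named.** SAP Section 2 gives CLcr limits for all three impaired groups, ending with "severe renal impairment (defined as $CL_{cr} < 30$ mL/min not requiring dialysis) who are otherwise healthy". The next section carries the caption "Table 1. Group Assignment Based on Creatinine Clearance Estimates".

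**Where eGFR is named.** The limits column of that same table is headed as eGFR. SAP 2.1 then prints the MDRD equation. It says the MDRD value "for renal disease classification or subject assignment into different renal disease groups should be multiplied by" the subject's BSA/1.73 m², because "renal elimination capacity is related to absolute glomerular filtration rate (GFR) in mL/min". It fixes the final group: "The eGFR value within 24 hours prior to lorlatinib dosing will be the value used for final subject stratification, group assignment, and PK analysis". Cockcroft-Gault CLcr is computed in addition and recorded, and no assignment role is given to it. In Protocol 1.4 the sentence that corresponds to the SAP Introduction reads "severe renal impairment (defined as eGFR $<$ 30 mL/min not requiring dialysis) who are otherwise healthy". Protocol 3.1 (Table 4), 4.1.2 and 4.1.3 also use eGFR.

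**The regression.** SAP 8.1: "The relationship between PK parameters and renal function (eGFR) will be determined by a linear regression model". SAP 8.2: "Both eGFR obtained from the MDRD equation and" Cockcroft-Gault CLcr, both from Day -1, are the regressors for CL/F and CL_R. Protocol 9.2.2 names the same two regressors for CL/F. None of these three places gives a unit for eGFR.

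**The concern.** Renal function group is the explanatory variable of the whole study. The SAP computes CLcr only by Cockcroft-Gault, so a CLcr definition of the groups, read literally, is a different classification from absolute MDRD eGFR. If an analyst regrouped subjects by it, the primary comparison of each impaired group with normal would be made on different sets of people. A milder risk is that the wrong definition is copied into table footnotes or the study report.

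The regression question is separate. The MDRD equation as printed returns mL/min/1.73 m². The BSA conversion is prescribed for classification and assignment, and SAP 8.2 refers only to the value obtained from the MDRD equation. An analyst could therefore regress CL/F on the indexed value while the group limits are in absolute mL/min. A subject correctly placed in Group B could then plot below 60, and the slope would depend on a choice not written down.

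**Working it through.** The plan states no figure to reproduce here, so the check compares the texts and then sizes the differences with the SAP's own formulas.

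**1. Which text assigns subjects?**

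| Place | Measure | Function of the text |
|---|---|---|
| SAP 2 | CLcr | background description |
| SAP Table 1, title | CLcr | caption |
| SAP Table 1, column header | eGFR | the limits themselves |
| SAP 2.1, equations | MDRD × BSA/1.73 | computation for assignment |
| SAP 2.1, stability paragraph | eGFR within 24 h before dosing | final group and PK analysis |
| Protocol 3.1, 4.1.2, 4.1.3 | MDRD eGFR | enrolment and final group |

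Every text that instructs someone to classify a subject uses eGFR. The CLcr wording appears only in a description and a caption. Protocol 1.4 does use CLcr limits, but for the earlier population PK analysis, which is a plausible source of the slip.

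**2. Are the two measures interchangeable?** They are not. Assumed subject: man, not African American, 50 y, 78 kg, 176 cm, serum creatinine 1.55 mg/dL.
- MDRD: 175 × 1.55^-1.154 × 50^-0.203 = 175 × 0.6031 × 0.4520 = 47.7 mL/min/1.73 m²
- BSA: 78^0.425 × 176^0.725 × 0.007184 = 1.943 m², and 1.943/1.73 = 1.123
- Absolute eGFR: 47.7 × 1.123 = 53.6 mL/min (moderate)
- Cockcroft-Gault: (140 - 50) × 78/(72 × 1.55) = 7020/111.6 = 62.9 mL/min (mild)

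The slip would therefore matter if anyone acted on it. By step 1, this subject is enrolled, dosed and analysed in Group C.

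**3. What does the SAP imply about the regressor's scale?** SAP 2.1 names one eGFR value for both group assignment and PK analysis. The value used for assignment is the absolute one, so the ordinary reading is mL/min. The wording in SAP 8.2 and Protocol 9.2.2 leans the other way, because the printed equation returns the indexed unit. The scale is implied but not stated.

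**4. What does the choice of scale change?** Write r = BSA/1.73, so absolute eGFR = r × indexed eGFR. If CL/F = a + b × absolute eGFR, then CL/F = a + (b × r) × indexed eGFR. If r were the same for everyone, the slope would be multiplied by r and the fitted CL/F values would be identical. Only variation in r between subjects alters the fit.

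- Example: man, not African American, 60 y, 80 kg, 175 cm, creatinine 1.3 mg/dL. Indexed 56.3; r = 1.956/1.73 = 1.131; absolute 56.3 × 1.131 = 63.7. He is in Group B but would plot below 60 on an indexed axis.
- Values of r: 51 kg and 150 cm gives about 0.84; 110 kg and 178 cm gives 1.31. These are examples and not limits. Eligibility sets no height limit, and 130 kg at 190 cm (BMI about 36) gives about 1.48.
- Simulated 32-subject trials (8 per group, assumed CV 25-35%, mean BMI 24-30): using the indexed value shifts the mean CL/F slope by 0-8%. The 10th-90th percentile range of the single-trial slope ratio is 0.88-1.21. The slope's own standard error is about 24-34% of the slope.

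**5. What depends on it?** The primary endpoints, AUCinf and Cmax, are compared by one-way ANOVA on group, and the regressor's scale does not enter. CL/F and CL_R are tertiary endpoints (Protocol 2). SAP 4.1 and 4.2 set no hypotheses or decision rules.

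**The case for a change.** The strongest case for acting is that the key variable of the study is misnamed in the current SAP, that the correction is a few words, and that an unstated unit makes the regression slope, and any prediction at a given eGFR, hard to reproduce. A single trial's slope ratio can lie well away from 1, and the indirect pointers on scale disagree.

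Part of this stands. The wording in SAP Section 2 and the Table 1 title is wrong, and SAP 8.2 could name the unit. It does not follow that the analysis is at risk. Counts of how many subjects would change group under Cockcroft-Gault describe a classification that no operative text calls for, so they do not measure harm. A projected change in the exposure ratios has the same defect. It would also have to place the clearance medians of Protocol 1.4, which belong to CLcr categories, on an eGFR axis, and extrapolate to severe impairment, where that analysis had one patient. On reproducibility, the report can label the axis, and both component values can be computed from recorded data. The analysis code in SAP Appendix 1 is redacted and may already settle the scale. Protocol 9 also lets the SAP carry such detail without a protocol amendment.

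**Conclusion.** No change to the plan is called for. The creatinine clearance wording in SAP Section 2 and the Table 1 title is a clerical slip. The table's own column, the equations, the final-assignment rule and the protocol all fix the groups by absolute MDRD eGFR, so correcting the slip would alter no group, no estimate and no confidence interval.

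The regressor's unit is a gap that an analyst fills sensibly. SAP 2.1 ties the eGFR for PK analysis to the value used for assignment, which is in absolute mL/min. If the indexed value were used, the regression would still be valid on its own scale. The expected shift in the mean CL/F slope is 0-8%, small beside a standard error of about 24-34% of that slope, and it touches tertiary parameters only. Those percentages rest on assumed body sizes, a 25-35% CV and 8 subjects per group. The conclusion on the primary ANOVA rests on the text alone and needs none of them.
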